Study Title:

Intercostal Liposomal Bupivacaine for the Management of Blunt Chest Wall Trauma

Research Team:

Principal Investigator:

[name]

Co-Principal Investigator:

[name]

1. Length of time for research

- a. Subject enrollment, data collection, and regulatory reporting: 18 months
- b. Statistical analysis of data: 2 months
- c. Manuscript and poster preparation, writing, and publication: 4 months

2. Research Location(s): University of Cincinnati Medical Center (UCMC) and UC Medical Science Building

3. Abstract/Brief Overview:

Polytrauma patients with rib fractures are at risk for poor pain control resulting in adverse pulmonary outcomes, including the development of pneumonia or respiratory failure. Liposomal bupivacaine provides a novel medication and administration route that may prevent the need for rescue intubation and development of pneumonia, avoid epidural use, and improve overall patient satisfaction and pain control. This study plans to enroll adult, polytrauma patients with blunt chest wall trauma resulting in rib and/or sternal fractures to receive either liposomal bupivacaine or normal saline intercostal nerve injections in addition to current standard of care (including intravenous, oral, or epidural narcotics). Patients will be excluded if they have a known allergy to bupivacaine, respiratory failure requiring intubation within 24 hours of enrollment, have a known atrioventricular nodal blockade process, hemodynamic instability, active myocardial infarction, greater than 20 rib fractures, or if they are pregnant or actively incarcerated. The purpose of this study is to evaluate the efficacy of liposomal bupivacaine to provide analgesia via posterior intercostal nerve block following significant blunt chest trauma, minimizing adverse outcomes and length of stay and overall narcotic use. The primary outcome of this study is to compare opioid requirements between groups. Secondary outcomes include comparison of clinical outcomes and treatment failures (e.g., development of pneumonia; median patient analgesic score by verbal numerical rating scale [NRS]; median time to first breakthrough opioid dose; incentive spirometer [IS] ability; intensive care unit [ICU] length of stay [LOS]; hospital LOS; use of additional analgesia adjuncts) and to perform a cost effective analysis.

4. Purpose of Study:

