The primary purpose of this pilot study is to compare opioid requirements between groups receiving intercostal liposomal bupivacaine to standard of care for acute traumatic pain related to blunt chest wall trauma with resultant rib and/or sternal fractures. Pain scores will be evaluated using the NRS (Appendix). Uncontrolled analgesia following rib fractures can result in intubation, pneumonia, prolonged length of stay, and death. Achieving adequate pain control in native airway patients prevents clinical challenges. Multimodal analgesia regimens are necessary to optimize patient outcomes and prevent untoward

effects of opioid analgesia. Liposomal bupivacaine offers a novel therapy that may revolutionize pain management in patients with rib fractures. Pain control with one injection may provide analgesia for up to 96 hours through a unique mechanism of action and site of application. Overall, the combination of a nonopioid analgesic, liposomal bupivacaine, with standard of care may lead to improved analgesia with fewer adverse effects. Specific aims include to 1) compare opioid requirements (in morphine equivalents) between patients with blunt chest wall trauma and rib and/or sternal fractures receiving liposomal bupivacaine versus standard of care; 2) compare clinical outcomes and treatment failures including development of pneumonia, median patient analgesia score using verbal NRS, median time to first breakthrough opioid dose, IS ability, ICU LOS, hospital LOS, and use of additional analgesic adjuncts; 4) and to perform a cost-effectiveness analysis

5. Background:

Background and Significance

Blunt chest wall trauma remains the second most common injury observed in non-intentional injury-related death in the U.S.A. and accounts for 10% of trauma-related emergency department visits worldwide.¹⁻³ Current literature has identified high morbidity and mortality rates for patients suffering from blunt chest wall trauma, with mortality ranging from 4 to 20%.^{2,4} The prevalence of rib fractures among blunt chest wall trauma patients requiring hospital admission is 4 to 10%.⁵ One of the most prominent contributing factors to blunt chest wall trauma morbidity is pain.⁶⁻⁸ The management of resultant pain serves as a core intervention in managing these patients.⁸

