emergency medicine and surgery practitioners are familiar with intercostal blocks for placement of tube thoracostomy. Intercostal blocks do not require additional training, as would be done in the setting of a pain medicine fellowship, and do not incur the risks of hypotension associated with epidural catheters. Additionally, intercostal and paravertebral blocks carry similar risks of pneumothorax or intercostal neurovascular bundle injury.

Study design:

This is an investigator-initiated, single-center, prospective, double-blinded, placebo-controlled trial funded by the United States Air Force. Multi-system, adult trauma patients greater than or equal to 18 years of age admitted to the University of Cincinnati Medical Center (UCMC), an urban American College of Surgeons-verified Level 1 trauma center with more than 3500 annual trauma admissions annually will be identified by the research team. Patients will be screened and those who meet all inclusion/exclusion criteria will be approached for informed consent by study personnel in their rooms. Informed consent will be obtained prior to enrollment and any study procedures are done. Patients will then receive either receive 1 mL of liposomal bupivacaine just below each affected rib or 0.9% sodium chloride peri-intercostal subcutaneous injection (as placebo control) via a 25-G needle. Goal enrollment is 200 patients with 100 patients in each group. Patients included in the study will be followed during inpatient hospitalization through discharge.

6. Research data collection/study procedures:

Intervention

Patients will be identified on admission and will be screened by inclusion/exclusion criteria. After informed consent is obtained they will be randomized into one of two possible groups:

- a. Liposomal bupivacaine intercostal (group 1; interventional)
- b. 0.9% sodium chloride peri-intercostal subcutaneous (group 2; placebo-control)

Patients will be placed on continuous monitoring of heart rate, EKG, and pulse oximetry. Blood pressure and respiratory rate will be measured every 5 to 10 minutes during the procedure and every at least 15 minutes for the first hour after the procedure. All patients undergoing injection will remain on heart rate, EKG, and pulse oximetry monitoring by telemetry for 96 hours following injection.

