A chest xray will be obtained as clinically indicated following the procedure if there is concern for the development of pneumothorax.

Self-reported pain will be measured using the verbal NRS, a 0-10 ordinal scale (e.g., 0 = "no pain"; 10 = "worst pain imaginable").²⁷ Breakthrough opioid dosing

will be guided by a formal inpatient analgesia protocol. Pain assessments will occur every 6 hours or per standard of care for the appropriate setting (e.g., intensive care unit, trauma ward) for the first 96 hours. All opioid dosing will be converted to oral morphine equivalents for comparison purposes. Time to first breakthrough opioid dose will be recorded. Incentive spirometry will be used and assessed and recorded by respiratory therapist, with adjunct inspiratory assistance (e.g., EzPAP) applied per our institutional volume expansion protocol.

Follow-up will occur daily by study coordinators and trauma service physicians for the first 96 hours after block procedure, then daily by the trauma service physicians for 14 days or until discharge from the hospital if it occurs earlier.

Standard of care analgesia regimen on the trauma service will be provided to all patients enrolled in the study, regardless of liposomal bupivacaine or placebo injection. This regimen will be per the Trauma acute multimodality pain management protocol (Appendix).

Typical escalation of analgesics provided for these patients, as deemed medically appropriate based on age and comorbid medical conditions, includes (in order of addition to regimen):

- Acetaminophen, oral or enteral
- NSAIDs, ibuprofen or ketorolac
- Lidocaine 5% transdermal patch
- Oral or enteral tramadol
- Oral or enteral hydrocodone or oxycodone
- IV morphine or hydromorphone, intermittent dosing
- Patient controlled analgesia morphine or hydromorphone
- Long-acting narcotics, including methadone, oxycodone ER, or morphine ER
- Neuromodulating adjuncts, including gabapentin or pregabalin
- Epidural analgesia catheter placement

During this time all adverse events will be recorded. Subjects who experience serious adverse events will be followed until the event resolves. If necessary these patients will be followed up by weekly phone calls as well as at the standard of care clinic visit two weeks post-discharge.

Randomization

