Myalgia	No interference with activity	Some interference with activity	Significant; prevents daily activity	ER visit or hospitalization

Table 9.4 extracted from: Guidance for Industry, Toxicity Grading Scale for Healthy Adult and Adolescent Volunteers Enrolled in Preventive Vaccine Trials, U.S. Department of Health and Human Services, Food and Drug Administration, Center for Biologics Evaluation and Research, August 2016

Treatment of cardiovascular and neurologic adverse events

- Local anesthetic systemic toxicity
 - Treatment will be initiated as recommended as the American Society of Regional Anesthesia and Pain Medicine, according to the society's checklist (Appendix)
- Treatment will include: transfer to intensive care unit setting if not already in intensive care unit, continuous hemodynamic monitoring for at least 24 hours, appropriate airway management with assistance from respiratory therapy and a critical care consultant as needed, cardiovascular stabilization and assistance from a critical care consultant as needed, administration of Lipid Emulsion therapy, as per ASRA checklist in Appendix, Neurology consult for any observed systemic neurologic toxicity (including change in vision, mental status change, persistent headache, seizure), Cardiology consult for any arrhythmias that persist greater than 30 minutes, beyond initial appropriate medical treatment, or result in hypotension with systolic blood pressure < 80mmHg.

10. Data Safety monitoring plan and/or DSMB:

Patients will be screened for the adverse events described above.

Adverse events will be continuously assessed on an ongoing basis by [name], medical monitor. Study will be stopped if:

- **Adverse events probably/likely or certainly related to study drug, regardless of severity, occur in > 10% of enrolled patients, or**
- **Serious/life-threatening adverse events, regardless of causality, occur in > 2% of enrolled patients.**

11. Data Analysis:

Primary Endpoint

- 1) Compare opioid requirements (in morphine equivalents) between trauma patients with rib and/or sternal fractures receiving liposomal bupivacaine versus standard of care.

Secondary Endpoints

- 1) Compare clinical outcomes and treatment failures including:
 - a. Development of pneumonia, defined as >100,000 cfu/mL bacteria on bronchoalvelolar lavage, or clinically with leukocytosis, pulmonary infiltrate and fever
 - b. Median patient analgesic score by verbal NRS

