This project will use Medidata Rave® as its Electronic Data Capture (EDC) software, which is a robust EDC platform for capturing, managing and reporting clinical research data. This system includes a robust query management system based on the Data Quality Plan, which will identify data quality checks to be programmed into the database design. Frequent monitoring of the database throughout the study will allow for corrective action to be taken quickly if problems are identified with the data collection process. The database will be password protected and appropriately secured such that only authorized study personnel will have access to the data. Data will be maintained in a confidential manner with regular reminders of the need for confidentiality provided from the senior investigator. A single subject log will be kept by the principal investigators for matching patient study number, initials, medical record number, and admission date (attached). Once assigned to the log, patients will only be evaluated using their de-identified, study number. Data entered into the electronic database will be de-identified.

Once the study has been completed, the subject log will be destroyed and only the de-identified electronic database will be kept. Only study personnel will have access to the data.

13. Study Population

UCMC is an urban, academic American College of Surgeons-verified Level 1 trauma center that treats over 3500 trauma patients each year. Patients admitted to the UCMC trauma service are eligible for enrollment. Patients will be screened on admission or identified per the daily trauma census. Trauma team

physicians may also contact study personnel daily once a patient is identified as a potential candidate. Study personnel will screen subjects for inclusion and exclusion. If patient meets inclusion criteria, then consent will be administered by study personnel (see section 14).

Inclusion Criteria

- a. Patients with an anticipated length of stay of at least 72 hours
- b. Trauma patients with two or more rib or sternal fractures
- c. Patients demonstrating the inability to achieve greater than 50% predicted inspiratory capacity based on ideal body weight using IS within the first 24 hours of admission (Appendix)
- d. Adults age 18 and older

Exclusion Criteria

- a. Patients with a known allergy to bupivacaine
- b. Respiratory failure requiring intubation within 24 hours prior to enrollment

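### Pain endpoint 1b is an overall 0-10 score with no body site or activity stated, in polytrauma patients, so it can understate the block's effect on chest-wall pain

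*Combined protocol and SAP*

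**What the plan says.** - **Aim.** Section 4 (Purpose of Study) sets the target as "acute traumatic pain related to blunt chest wall trauma with resultant rib and/or sternal fractures" and refers to the Appendix for the NRS.
- **Instrument.** Section 6 (Intervention): "Self-reported pain will be measured using the verbal NRS, a 0-10 ordinal scale". The anchors are generic, running from absence of pain to the worst conceivable. On procedure, the text gives timing only, for the first 96 hours: "Pain assessments will occur every 6 hours or per standard of care for the appropriate setting". The Data Collection paragraph refers back to this description.
- **Endpoint.** Section 11, secondary endpoint 1b: "Median patient analgesic score by verbal NRS".
- **Population.** Section 3: "This study plans to enroll adult, polytrauma patients with blunt chest wall trauma". Section 5 (Study design): "Multi-system, adult trauma patients greater than or equal to 18 years of age". The injury criterion in section 13 is "Trauma patients with two or more rib or sternal fractures". Severe traumatic brain injury is the only other injury named as an exclusion.
- **Treatment site.** Section 6 places the active injection at the intercostal bundle of each affected rib.
- **Analysis.** Section 11 compares continuous outcomes with t-test/ANOVA or rank-based tests and names no covariates. Injury severity score and chest abbreviated injury score are collected (section 6) but given no role in the analysis.

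**The concern.** The question concerns chest-wall pain, and the treatment works only at the chest wall. A patient with several injuries who is asked for one unspecified number may answer for a limb or spine fracture, which an intercostal block cannot relieve. A score given while lying still may also miss pain on deep breathing, although the protocol's rationale is that better analgesia improves breathing and spirometry.

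Endpoint 1b is the only direct measure of pain. Opioid use, the primary outcome, is also driven by all injuries and cannot supply chest-specific evidence in its place. If 1b showed no difference, the reader could not tell a block that failed from a score that followed other injuries. Site-specific pain cannot be reconstructed once the data are collected.

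**Working it through.** **1. Is there a figure in the plan to reproduce?** No. The documents give no expected NRS difference, no NRS standard deviation and no power for endpoint 1b. The sample-size statement in section 11 concerns opioid use in mg. Only its 100 patients per arm is used here.

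**2. What the text settles.** Of the places that mention the NRS (sections 4, 6 and 11), none that is legible gives a site or activity. The eligibility list does not limit other painful injuries. The mechanism for attenuation is therefore present, but its size is not stated and must be assumed.

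**3. Simple dilution formula (assumed inputs).** Let w be the share of the chest-wall effect that reaches the overall score. With n per arm and a two-sided 0.05 test:

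power = Φ( w·δ / (SD·√(2/n)) − 1.96 )

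With n = 100, SD = 2 and δ = 1, the standard error is 2 × √0.02 = 0.283.
- w = 1: 1/0.283 − 1.96 = 1.58, power 94%.
- w = 0.5: 0.5/0.283 − 1.96 = −0.19, power 42%.

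The required sample size scales with 1/w², so halving the effect multiplies it by four (126 to 504 in total for 80% power). Across SD 2.0 to 3.0 and δ 1.0 to 2.0, power runs from 65% to over 99% at w = 1, and from 22% to 94% at w = 0.5.

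**4. Simulation with an explicit reporting rule (assumed inputs).** Chest pain is normal with mean 6 and SD 2, rounded and limited to 0-10. Some patients have another painful injury, also with SD 2. The reported score is the worse of the two. The block lowers chest pain only. There are 100 patients per arm, one score each, compared by rank-sum test at 0.05.

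| Other-site pain (share of patients, mean) | Difference seen, 1-point effect | Power, 1-point effect | Power, 1.5-point effect | Power, 2-point effect |
|---|---|---|---|---|
| Chest-wall score only | about 1.0 | about 93% | over 99% | about 100% |
| 50%, mean 4 | 0.84 | 87% | 99% | about 100% |
| 75%, mean 5 | about 0.65 | about 72% | 95% | over 99% |
| 100%, mean 6 | 0.42 | about 42% | 67-69% | about 85% |

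A milder case (25% of patients, mean 4, 1-point effect) gives a difference of about 0.9 and power of 89-90%.

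**5. Reading.** The loss is minor where chest pain dominates or the block effect is 1.5 to 2 points. It is large where other injuries hurt as much as the chest and the block effect is about 1 point. The documents do not say which case applies.

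**The case against.** - **The instrument is not fully visible.** The Appendix entry for the NRS survives only as a heading. Site wording could be there, so the statement must be limited to the legible text. This stands.
- **Eligibility selects important chest injury.** Patients must have failed to exceed 50% of predicted inspiratory capacity. That makes dominant chest pain more plausible and the last row of the table less so. This stands.
- **Overall pain is a legitimate outcome.** Other-site pain is balanced between arms in expectation, so the comparison of overall pain is valid and matters to patients. A reader might infer bias between the arms, and the documents do not support that. The supportable statement is attenuation relative to the chest-wall contrast.
- **Breathing function is measured elsewhere.** Incentive spirometry volume is endpoint 1d, and portable spirometry is done daily. A reader might infer that a working block would go undetected. That does not follow, because these measures are chest-specific and depend on effort. They record volume, however, and do not replace a pain score.
- **The pain-management protocol is general.** Its entries for limb and spine fractures and burns might be read as describing the enrolled patients. It is a trauma-service document and gives no frequency for this trial. The polytrauma and multi-system descriptions carry the point without it.
- **The simulation is simplified.** It uses one score per patient, whereas scores repeat over 96 hours, and every pain input is assumed. This stands as a limit on the size, not on the mechanism.

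**Conclusion.** The point holds as a limitation of one secondary endpoint in a self-described pilot. Followed as written in the legible text, endpoint 1b measures overall pain, while the stated aim is chest-wall pain. In patients whose other injuries are not restricted, this can attenuate the contrast of interest.

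The size is not determined by the documents. On the stated assumptions, the loss at a 1-point effect runs from about 6 percentage points of power (93% to 87%) to about 51 (93% to 42%). At 1.5 points it runs from almost nothing to roughly 30 points. These figures rest on the assumed chest-pain distribution, the share and severity of other pain, and patients reporting their worst pain. The point does not invalidate the randomised comparison. It is worth making because the remedy is cheap and is available only before data are collected.

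**What to change.** First check the NRS wording in the Appendix. If it names neither site nor activity:

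1. Add a chest-wall NRS, asked for the fracture site, at rest and on a deep breath, at least once daily for the first 96 hours. Use the existing daily coordinator follow-up or the incentive spirometry session, where the patient already takes the deep breath.
2. Define endpoint 1b on this score, and keep the routine overall NRS as a supporting measure.

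**Cost.** One or two extra verbal questions and CRF fields per day, with no extra staff or procedure. Over 96 hours, once-daily questioning means 4 × 2 = 8 responses per patient. Asking both questions at every 6-hourly assessment would mean up to 16 × 2 = 32, so once daily is the proportionate choice.

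The change does not alter the primary opioid outcome, which also reflects all injuries.

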Following informed consent, patients will undergo 2x1 block randomization to ensure equal allocation to each intervention group. Randomization will be performed by study personnel and will be blinded as there will be placebo injections for patients randomized into group two and the same number of injections would be used regardless of intervention arm.

Data Collection:

Verbal NRS, pain assessment data, opioid use, and time to first opioid breakthrough dose will be collected as previously described. Portable spirometry will be used daily to objectively and serially assess lung function. Additional data collection points include patient sex, age, weight, body mass index, body surface area, injury severity score, chest abbreviated injury score, and ICU and hospital length of stay. Safety will be evaluated by the occurrence of *a priori* serious adverse events. Costs will be evaluated utilizing hospital and pharmacy databases.

Schedule of subject identification and data collection

Subjects will be identified based on inclusion criteria at the time of admission to the trauma service following evaluation in the emergency department. Subjects meeting inclusion criteria will be enrolled within 6 hours of admission. Vitals monitoring will occur during the intercostal nerve block procedure and continue by telemetry for the next 96 hours or until hospital discharge, whichever occurs first.

7. Specimen collection:

No serum assays are necessary for this study and will not be collected.

8. Potential Benefits:

Blunt chest wall trauma remains a common injury seen in non-intentional injury-related deaths. It accounts for nearly 10% of trauma-related emergency department visits worldwide and is associated with high morbidity and mortality. This morbidity and mortality are influenced by the pain experienced by these events which can involve rib or sternal fractures as instigating stimuli.

Uncontrolled analgesia following rib fractures can result in intubation, pneumonia, prolonged length of stay, and death. Achieving adequate pain control in native airway patients prevents clinical challenges. Multimodal analgesia regimens are necessary to optimize patient outcomes and prevent untoward effects of opioid analgesia (e.g., hypotension; bradycardia; central nervous system depression; respiratory depression).

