 - c. Median time to first breakthrough opioid rescue dose
 - d. Incentive spirometry serial volume capacity
 - e. ICU LOS
 - f. Hospital LOS
 - g. Use of additional analgesia adjuncts
 - i. Epidural catheter
 - ii. Non-opioid analgesics (e.g., non-steroidal anti-inflammatory drugs; gabapentin; pregabalin; carbamazepine; ketamine; acetaminophen)
- 2) Perform a cost-effectiveness analysis
- 3) Calculate dose and exposure of lidocaine or bupivacaine over time from Lidoderm patches, intercostal nerve blocks, or epidural catheters

Statistical analyses will be performed using SAS. An intention-to-treat model will be used for data analysis. Patients randomized into the treatment arm will be included in the primary outcome analysis. Patients withdrawn from the study will have data included up to the point of withdrawal. Nominal data will be reported using frequencies of occurrence and proportions as appropriate. Continuous data will be reported using means and standard deviations or medians and

interquartile ranges as appropriate per distribution. Hypothesis testing for nominal data will be performed using the Fisher's exact test or chi square test as required based on sample size. Continuous data will be compared using student's t-test/ANOVA or rank sum/Kruskal-Wallis ANOVA for normally distributed and non-normally distributed data, respectively as appropriate. A p-value < 0.05 will designate statistical significance. Costs associated with the cost-effectiveness analysis will be pulled from hospital and pharmacy databases.

Given the pilot nature of the study, a total of 200 patients will be enrolled. Assuming a 96-hour requirement of 250-mg oral morphine equivalents (approximately 12.5-mg IV hydromorphone), we anticipate a 20% reduction to 200-mg oral morphine equivalents (approximately 10-mg IV hydromorphone) resulting in an expected difference in means of 50 mg and an anticipated standard deviation of 50 mg. To achieve an 80% power with an alpha of 0.05 for this primary outcome, the goal enrollment is 200 patients.

12. Data storage and confidentiality (include sample storage if applicable)

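### The daily spirometry endpoint has no stated analysis that fits a series, and the inspiratory reading taken for eligibility is left unused

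*Combined protocol and SAP*

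**What the plan says.** Section 11 lists among the secondary endpoints "Incentive spirometry serial volume capacity". Section 6, Data Collection, gives the schedule: "Portable spirometry will be used daily to objectively and serially assess lung function". Neither place says how long the daily readings continue, which day or window counts, or how a patient's readings become one result.

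For every continuous outcome, Section 11 offers the same methods: "Continuous data will be compared using student's t-test/ANOVA or rank sum/Kruskal-Wallis ANOVA for normally distributed and non-normally distributed data". It names no repeated-measures method and no covariate.

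Section 13, inclusion criterion c, admits "Patients demonstrating the inability to achieve greater than 50% predicted inspiratory capacity based on ideal body weight using IS within the first 24 hours", counted from admission. Eligibility is settled before consent, and consent before randomisation (Sections 5 and 14), so every correctly enrolled patient has a pre-randomisation inspiratory reading. It does not appear among the data items in Section 6 or in the analysis in Section 11.

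For pain, Section 6 says "Pain assessments will occur every 6 hours or per standard of care for the appropriate setting" over the first 96 hours, and the endpoint in Section 11 is "Median patient analgesic score by verbal NRS".

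**The concern.** The named tests compare two sets of independent values, but the spirometry endpoint supplies several correlated values per patient. Something must happen between the data and the test, and the plan does not say what. An analyst could reduce each series to one number, pool all days, or test day by day. The first route is valid if the summary is fixed in advance. The second treats correlated readings as independent. The third gives several chances of a positive result. If the choice is made after the data are seen, the reported p-value is hard to interpret whichever route is taken.

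The second issue is efficiency. The reading that defines eligibility is a natural covariate for the same measurement after the block. An unadjusted comparison remains valid in a randomised trial, but it leaves out information that screening has already produced.

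**Working it through.** **Plan's own figure.** There is none to reproduce. The sample-size paragraph in Section 11 concerns 96-hour opioid use only, and no effect size, standard deviation or correlation is given for spirometry.

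**Inputs from the documents.** Daily readings (Section 6, Data Collection), 200 patients at 100 per arm (Section 5), significance at p < 0.05 (Section 11).

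**Assumptions.** Two-sided testing, since sidedness is not stated. Within-patient correlation between days, and correlation ρ between the qualifying reading and the patient's follow-up result, both shown over ranges. Four daily readings, which matches the 96-hour study follow-up, but no duration for spirometry is given.

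**1. Gain from baseline adjustment.** Variance factor = 1 − ρ². Unadjusted equivalent of 200 patients = 200 / (1 − ρ²).

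| ρ (assumed) | Variance factor | Cut | Unadjusted equivalent of 200 |
|---|---|---|---|
| 0.2 | 0.96 | 4% | 208 |
| 0.3 | 0.91 | 9% | 220 |
| 0.5 | 0.75 | 25% | 267 |
| 0.7 | 0.51 | 49% | 392 |

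Criterion c keeps only patients at or below half of predicted. That narrows the range of % predicted and tends to lower ρ, so the upper rows may be optimistic on that scale. The restriction bites less on raw volume. Predicted values in the Appendix nomogram run from 1250 to 4000 mL, so the 50% ceiling itself runs from 0.5 × 1250 = 625 mL to 0.5 × 4000 = 2000 mL, depending on sex, age and height.

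**2. If days were pooled as independent readings.** Design effect DE = 1 + (m − 1) × correlation. True type I error = 2 × [1 − Φ(1.96 / √DE)]. With m = 4:

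- Correlation 0.3: DE = 1.9, 1.96/√1.9 = 1.42, error 16%.
- Correlation 0.5: DE = 2.5, 1.96/√2.5 = 1.24, error 22%.
- Correlation 0.7: DE = 3.1, 1.96/√3.1 = 1.11, error 27%.

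The result depends on m. With three readings (DE = 2.0 and 2.4 at correlation 0.5 and 0.7), the error is 17% and 21%.

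**3. If each day were tested separately.** For four independent tests, 1 − 0.95⁴ = 0.185, about 19%. This is an upper bound. With equally correlated test statistics, the chance of at least one |z| above 1.96 in four is about 16% at correlation 0.5 and 13% at 0.7.

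**4. If one pre-set value per patient is used.** The named tests are valid and steps 2 and 3 do not arise. What remains is the unused baseline in step 1.

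**The case against.** The strongest reply is that the plan is silent rather than wrong. A per-patient summary such as a mean, a change or the value on a set day fits the tests in Section 11, and nothing commits the analyst to pooling or daily testing. Unadjusted comparison is valid under randomisation, so adjustment is a matter of efficiency. The qualifying reading is also not an ideal covariate. Eligibility truncates its range, it is not a listed data item, and Section 6 calls the daily measurement portable spirometry without saying that it is the same measurement as the incentive spirometry in the endpoint. All of this stands. It makes the point one of under-specification and lost precision, not of a demonstrably invalid test.

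A reader might go further on pain scores and infer three things. None is supported.

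- **Gross error inflation.** Pooling 16 six-hourly scores at correlation 0.3–0.7 would give 40–56% type I error, but no section says that scores will be pooled. The endpoint wording reads naturally as one median per patient. In simulation, a rank-sum test on such medians held 3.8–5.7%.
- **Invalidity from uneven scoring frequency.** Frequency may vary by setting, but this disturbs per-patient medians only if it differs by arm. In simulation with pain falling over time, dense early scoring in 30% versus 50% of patients left rejection at 4.8%. It took 20% versus 60% to reach 10.1%, with a shift of 0.18 points. The documents give no sign of such an imbalance.
- **A wasted baseline pain score.** No pre-block score is explicitly scheduled, so the unused-baseline argument applies to spirometry only.

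**Conclusion.** The point holds for spirometry. A daily series is paired with tests that take one value per patient, no rule connects the two, and the pre-randomisation reading required for eligibility is ignored.

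The firm gain is precision: a variance cut of 4–9% if ρ is 0.2–0.3 and 25–49% if it is 0.5–0.7. These correlations are assumed, and the lower range is plausible given the selection on % predicted. The error rates for pooling (about 22–27%) and for daily testing (at most 19%, less when days are correlated) describe routes that the plan leaves open, not routes that it adopts. Both figures also assume four readings.

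For pain, the documents support only a request for confirmation. Both endpoints are secondary and the study describes itself as a pilot. The change is worth making because it is cheap, and nothing here bears on the primary opioid comparison.

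**What to change.** **Spirometry.** In Section 11, specify one repeated-measures model of daily inspiratory volume (or % predicted, naming the reference used). Include arm, day, arm-by-day and the qualifying reading as covariate, with correlation within patient allowed for. State the window and name in advance the one contrast to be tested, for example the arm difference averaged over that window. Present day-by-day estimates as description only. State how series cut short by discharge or withdrawal are handled. Confirm that the qualifying and daily readings are the same measurement.

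**Pain.** Add one sentence confirming that the endpoint is one median per patient over 0–96 hours, compared between arms by the rank-sum test.

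**Cost.** SAP wording and slightly more programming. The qualifying reading is already obtained for eligibility, but its value should be added to the listed data items so that it reaches the database. No extra patients or visits are needed.
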